We *hypothesize* that subclinical eukaryotic viruses will be associated with negative IVF cycle outcomes.

C3 Rationale for the Selection of Outcome Measures

We expect to define the clinical impact of withholding antibiotic prophylaxis before embryo transfer as measured by markers of a successful IVF cycle. As we hypothesize that withholding prophylaxis will be non-inferior to routine antibiotic administration, these results are expected have a positive clinical impact by decreasing unnecessary broad-spectrum antibiotic exposure and potentially creating a paradigm shift in IVF protocols.

D Study Design

D1 Overview or Design Summary

This will be a prospective randomized controlled non-inferiority trial in which 178 couples will receive the standard of care prophylactic antibiotics (control) and 178 will not receive prophylactic antibiotics (experimental). The primary outcome is clinical pregnancy rate. The expected primary outcome is that withholding prophylactic antibiotics will be non-inferior to antibiotic prophylaxis in terms of clinical pregnancy rate. Secondary outcomes include spontaneous miscarriage rate and embryo development as measured by fertilization rate, blastocyst conversion rate, blastocyst utilization rate, and live birth rate.

D2 Subject Selection and Withdrawal

2.a Inclusion Criteria

The female partner must be aged 18–43 years and going through a fresh IVF cycle. The male partner must be aged 18 at minimum. There is no upper age limit to males.

2.a Exclusion Criteria

Couples will be excluded from enrollment if they have any contraindication to antibiotic treatment (ie: allergy), are not intending to undergo embryo transfer (fertility preservation patients and oocyte donors), require use of extended antibiotic coverage at time of egg retrieval, are already on antibiotics for any reason (e.g., upper respiratory infection), have a recent history of pelvic infection, or are planning on limited insemination (inseminating a limited number of the eggs retrieved).

2.b Ethical Considerations

Participation will be completely voluntary. Patients care will not be impacted in any way by their decision to participate or lack thereof. Incidence of pelvic infection following embryo transfer approaches zero in this low risk population therefore patients are not being placed at any additional undo risk. They may be spared from experiencing potential adverse side effects of the oral antibiotic.

2.c Subject Recruitment Plans and Consent Process

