partners. Patients may be hesitant to deviate from our previous standard of care. On the other hand, patients may want to avoid additional medication and may not take the antibiotic regardless to which arm they are randomized. We would mitigate this risk by a thorough informed consent and expressing our goal is to improve our current IVF protocols and that the best approach is not known while emphasizing the importance of compliance. Reportable severe events include development of pelvic infection following embryo transfer, a significant increase in spontaneous miscarriage rates or a note in increased contamination rates in the lab. Risks of pelvic infection in this low risk population following embryo transfer is remarkably rare as stated above and we do not anticipate this occurring. We anticipate miscarriage rates to be equivalent or improved in the non-prophylaxis group. The lab uses genatmicin routinely in embryo culture media to decrease contamination rates and will continue to be closely monitored for any increase in contamination rates. Reportable non-severe adverse events include yeast vaginitis, nausea and vomiting or other adverse reactions from antibiotic prophylaxis.

Obtaining a mid-vaginal swab poses little to no risk to the patient. The patient may experience some slight discomfort from one additional speculum exam at the time of baseline testing. The embryo transfer catheter tip will be sequenced for comparison to the vaginal swab following embryo transfer and will require no additional invasive testing or exams.

2.f Early Withdrawal of Subjects

While loss to follow up is extremely rare in this circumstance, some patients who are enrolled and randomized may not make it to egg retrieval or may not get an embryo transfer due to either a poor response to medications or poor embryo quality. We will account for these patients in our 5% drop out estimation and they will not be included in analysis.

2.g When and How to Withdraw Subjects

Patients can withdraw from the study at any time if they choose to do so. Their care will not be impacted by their participation or lack thereof.

2.h Data Collection and Follow-up for Withdrawn Subjects

Subjects who withdraw will not be included in the final data analysis.

D3 Study Drug –

3.a Description

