Azithromycin is routinely given to both partners (in male/female couples) or to the embryo recipient in same sex couples or gestational carriers when they start their IVF cycle medications and is our current standard of care.

3.b Treatment Regimen

1 gram oral azithromycin, once the day of IVF cycle start (when they start injectable gonadotropin medications) which is our current standard of care.

3.c Method for Assigning Subjects to Treatment Groups

Computer random number generator.

3.d Preparation and Administration of Study Drug

Azithromycine will be prepared and dispensed by the patients preferred pharmacy as is standard practice if they are randomized to the antibiotic prophylaxis group.

3.e Subject Compliance Monitoring

Patients will give verbal confirmation of compliance.

3.f Blinding of Study Drug

Patients will not be blinded to which group they're in. A placebo control will not be used.

3.g Receiving, Storage, Dispensing and Return

Azithromycin will be prepared and dispensed by the patients preferred pharmacy as is standard practice if they are randomized to the antibiotic prophylaxis group.

E Study Procedures

E1 Screening for Eligibility

Couples will be screened for eligibility by their primary physician, the primary investigator, [name] or the Research Project Coordinator. If they meet the inclusion and exclusion criteria they will be offered enrollment.

E2 Schedule of Measurements

Outcomes measures are routinely tracked by our clinical to report to the Society of Assisted Reproductive Technology (SART). Patients who participate in the study will not be required to make any additional visits beyond consent.

E3 Visit 1

Outcome measures for specific aim 3 will be tracked from the patients initial oocyte retrieval and embryo transfer visit. The lab routinely tracks this data and no additional query or visits will be required in term of embryo development data.

E4 Visit 2 etc.

Specific Aim 1 will be addressed and tracked when patients come in for their viability ultrasound at 6-7 weeks gestation which is routine practice in our clinic. Clinical pregnancy is defined as a gestational sac, with fetal pole and cardiac activity, on

ultrasound. No additional visits will be required. Patients will continue to be tracked once they are released from our practice to their primary OBGYN to track miscarriage rate (spontaneous loss prior to 20 weeks) and subsequent live birth outcomes.

Schedule of Visits for Microbiome/Virome Study:

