Outcome measures will be assessed the same as th above aforementioned schedule of measurements for the noninferiority trial. Collection of specimens for the exploratory study will occur as described below:

Visit 1-

Women enrolled in the smaller exploratory study will have a midvaginal swab obtained when they get their baseline testing prior to ultrasound. This visit is already required in the IVF cycle and will not require an additional visit to collect the specimen.

Visit 2-

The second specimen will be obtained with a midvaginal swab prior to egg retrieval. This visit is already required in the IVF cycle and will not require an additional visit to collect the specimen.

Visit 3-

The third and final specimen will be obtained via midvaginal swab prior to embryo transfer. This visit is already required in the IVF cycle and will not require an additional visit to collect the specimen. When the male partner produces a sample for use for IVF at this time, a 100 microliter volume will be obtained and frozen separately. No additional visit will be required for them.

All specimen swabs collected for microbiome and virome profiling will be flash frozen at -80 celsius until all specimens have been collected and can be batch analyzed at the same time.

E5 Safety and Adverse Events

5.a Safety and Compliance Monitoring

As administration of 1 gram oral Azithromycin is standard of care in our practice no additional risk will be incurred from prescribing the antibiotic prophylaxis. Patients will be asked regarding compliance with medication administration and if any adverse side effects were incurred including yeast vaginitis, nausea and vomiting or other adverse reactions from antibiotic prophylaxis.

5.b Medical Monitoring

i Institutional Data and Safety Monitoring Board

In addition to principle investigator review of adverse events, a data and safety monitoring board (DSMB) will be established. This will include [name], [name], PhD, [name], MSCI and [name] and [name]. The designated group will meet once enrollment reaches 50% and then every 6 months thereafter to review occurrence of adverse events in addition to assessing recruitment progress and will review for futility of the trial in the context of lack of adequate recruitment.

5.c Definitions of Adverse Events

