Severe adverse events: pelvic infection (endometritis, cervicitis or pelvic inflammatory disease) as diagnosed by cervical culture and physical exam, spontaneous miscarriage (pregnancy loss prior to 20 weeks gestation) or increased contamination rates in the lab which is routinely monitored for by our embryologists.

Non-severe adverse events include adverse effects of antibiotic administration including yeast vaginitis, abdominal pain, diarrhea, nausea and vomiting.

5.d Classification of Events

Reportable severe events include development of pelvic infection following embryo transfer, a significant increase in spontaneous miscarriage rates or a note in increased contamination rates in the lab. Risks of pelvic infection in this low risk population following embryo transfer approaches zero and we do not anticipate this occurring. We anticipate miscarriage rates to be equivalent or improved in the non-prophylaxis group but will be closely tracked for any increase in incidence. The lab uses gentamicin routinely in embryo culture media to decrease contamination rates and will continue to be closely monitored as is standard for quality control measures in our lab for any increase in contamination rates.

Reportable non-severe adverse events include yeast vaginitis, nausea and vomiting or other adverse reactions from antibiotic prophylaxis which the patients will report to their nurses.

5.e Data Collection Procedures for Adverse Events

In addition to principle investigator review of adverse events, a data and safety monitoring board (DSMB) will be established. This will include [name], [name], [name] and [name] and [name], MSCI. The designated group will meet once enrollment reaches 50% and then every 6 months thereafter. Adverse events will be noted in the patients chart and in the redcap database for complete capture and tracking. Data will be analyzed if a noted increase in severe adverse events is noted or otherwise once enrollment reaches 50% and then every 6 months thereafter when the DSMB meets.

5.f Reporting Procedures

Patients will be instructed to report any adverse symptoms to their respective nurse or doctor. These events will be immediately reported to the PI or research project coordinator.

5.g Adverse Event Reporting Period

Until study completion.

-

F Statistical Plan

F1 Sample Size Determination and Power

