Intention-to-treat and per protocol analyses will be performed. Chi-squared and Fisher's exact tests will be used to compare categorical variables as appropriate. Kolmogorov-Smirnov test will be initially used to assess the distribution pattern of continuous variables. Normally distributed variables will be analyzed via Student's t-test. Non-normally distributed continuous variables will be analyzed with the Mann-Whitney U test. The primary analysis is based on difference in clinical pregnancy rate between the two groups. The sample size estimation for the study is based on this comparison with a non-inferiority approach as described above with an absolute difference of 15% or less to be considered non-inferior. Secondary analyses will include spontaneous miscarriage rate and embryo development. A subsequent interval analysis will assess live birth rate. Pearson's correlation coefficients will be used to quantify the association

between the two groups and embryo development. $P < 0.05$ will be considered statistically significant.

Each microbiota sample will have the taxon indicated as relative abundance. To assess the diversity across an IVF cycle, after log transformation, linear mixed regression will be applied. Wilcoxon rank sum will be used to measure for difference in richness and diversity with clinical outcomes of clinical pregnancy rate, miscarriage rate and embryo outcomes.

IBM® SPSS® statistics version 23 will be used for all analyses.

F5 Missing Outcome Data

All outcome data is required to be tracked by SART and no additional query will be required. We do not anticipate any issues with missing outcome data.

G Data Handling and Record Keeping

G1 Confidentiality and Security

Our practice is required to track patient demographic data and cycle outcome measures to report to the Society for Assisted Reproductive Technology (SART). Data is currently recorded and tracked through Research Electronic Data Capture (REDCap). REDCap is a secure web-based application designed to support data capture for research studies, providing 1) an intuitive interface for validated data entry; 2) audit trails for tracking data manipulation and export procedures; 3) automated export procedures for seamless data downloads to common statistical packages; and 4) procedures for importing data from external sources.¹⁸ Enrolled patients will be exported and tracked in a separate REDCap data set from our existing dataset.

G2 Records Retention

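### The exclusions in D2 2.f and 2.h have no safety exception, so a final adverse-event report that followed them would drop side effects already on record

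*Combined protocol and SAP*

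**What the plan says.** All references are to the combined protocol and SAP.

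- **Exclusions.** The whole text of D2 2.h is "Subjects who withdraw will not be included in the final data analysis". D2 2.f deals with randomised couples who miss retrieval or transfer because of poor response or poor embryos: "We will account for these patients in our 5% drop out estimation and they will not be included in analysis". Neither section mentions safety data.
- **Exposure.** D3 3.b gives the regimen as "1 gram oral azithromycin, once the day of IVF cycle start". There is no placebo, and D3 3.f says "Patients will not be blinded to which group" they are in.
- **Collection.** Under E5 5.a, patients are asked about compliance and "if any adverse side effects were incurred including yeast vaginitis, nausea and vomiting or other adverse reactions from antibiotic prophylaxis". E5 5.e adds: "Adverse events will be noted in the patients chart and in the redcap database for complete capture and tracking". E5 5.g runs reporting to the end of the study.
- **Review during the trial.** E5 5.b and 5.e have the DSMB review adverse events at 50% enrolment and every 6 months after that. F2 looks for a trend in severe outcomes in either group.
- **Final analysis.** F4 says "Intention-to-treat and per protocol analyses will be performed" but does not define either set. It names no safety population and no adverse-event table. Of the events in E5 5.c, it lists only miscarriage.

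**The concern.** The plan undertakes to record adverse events completely, then states a rule for the final analysis that discards some of those records. In the antibiotic arm, couples who withdraw after cycle start, or who fall under 2.f, will already have been prescribed the drug. Any early side effect can therefore precede the exclusion. Whoever writes the final safety summary finds no safety population in F4. The only explicit statements on who is left out are 2.f and 2.h, and these conflict with an intention-to-treat analysis.

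Side effects are part of the argument for withholding the drug. D2 2.b says of participants: "They may be spared from experiencing potential adverse side effects of the oral antibiotic". If pregnancy rates prove non-inferior, the side-effect count by arm is how that gain would be shown. A count that omits recorded events could understate the gain and disagree with what the DSMB saw.

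**Working it through.** **Inputs from the plan.** F1 gives 178 couples per arm, a 41% baseline pregnancy rate, a 15% margin, one-sided alpha 0.025, 80% power and 5% dropout. The plan gives no side-effect risk and no withdrawal rate among couples with side effects.

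**Step 1: reproduce the plan's figure.** With 41% assumed in both arms:

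n = (1.960 + 0.842)² × 2 × 0.41 × 0.59 / 0.15² = 7.851 × 0.4838 / 0.0225 = 168.8, so 169 per arm.

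169 / 0.95 = 177.9, so 178 per arm and 356 in total. This matches F1.

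**Step 2: denominators.** 5% of 178 is 8.9, so about 9 couples per arm are excluded and 178 − 9 = 169 remain. Section 2.f places its exclusions within the 5%. The plan does not say whether voluntary withdrawals are also within it, so 169 assumes that they are. If total exclusion were 10%, 15% or 20% (assumed), the retained denominators would be 160, 151 or 142.

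**Step 3: effect on the reported rate, azithromycin arm.** Let r be the true risk per couple and f the share of affected couples excluded. Unaffected couples are excluded at 5%.

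Reported rate = 178r(1 − f) / [178r(1 − f) + 178(1 − r) × 0.95]

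For r = 10% there are 17.8 events:
- f = 5%: 16.91 / 169.10 = 10.0%
- f = 10%: 16.02 / 168.21 = 9.5%
- f = 25%: 13.35 / 165.54 = 8.1%

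Reported rate, with events lost (178rf) in brackets:

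| Assumed risk r | f = 5% | f = 10% | f = 25% |
|---|---|---|---|
| 5% | 5.0% (0.45) | 4.7% (0.89) | 4.0% (2.23) |
| 10% | 10.0% (0.89) | 9.5% (1.78) | 8.1% (4.45) |
| 20% | 20.0% (1.78) | 19.1% (3.56) | 16.5% (8.90) |

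In the first column exclusion is unrelated to side effects. Events are lost there, but the rate does not move.

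**Step 4: heavier exclusion.** Suppose 15% are excluded (27 of 178) and the rate among the 151 retained couples is 10%, giving 15.1 events. If the excluded couples also have 10%, then 2.7 events are missed and the all-randomised rate is still 10.0%. If they have 20%, then 5.4 are missed and the all-randomised rate is (15.1 + 5.4) / 178 = 11.5%. The shift again comes from the link between side effects and exclusion.

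**The case against.** **The plan contains no final side-effect comparison.** The aims, the outcomes in D1 and the methods in F4 list none. A reader might infer that the plan commits to a biased comparison by arm. It does not: the error is conditional on someone writing such a report under 2.f and 2.h. This objection stands and limits the point. The rule and the missing table remain gaps, because data collected so fully will naturally be summarised at the end.

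**Safety is reviewed separately.** E5 and F2 set up a DSMB review that 2.h, which concerns the final analysis, does not restrict. A reader might infer that safety oversight misses these couples. The text does not support that. It is also reasonable to read 2.h as governing outcomes and E5 as governing safety, but the plan does not say so.

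**Side effects have little reason to cause withdrawal.** There is one dose, so no later dose to avoid, and E2 requires no visits beyond consent. Section 2.f calls loss to follow-up extremely rare and puts its exclusions down to response and embryo quality. This stands: harm-driven withdrawal is possible in an open-label trial, but nothing in the plan shows that it is likely.

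**All randomised couples is not the right denominator for every event.** Both partners take the drug in male/female couples but only one person does in same-sex couples (D2 2.d). Yeast vaginitis concerns women only. Sections 2.e and 5.d make pelvic infection reportable after transfer, so couples without a transfer would dilute that rate. This stands, and the fix allows for it.

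**Conclusion.** The point holds as a minor one. Sections 2.f and 2.h exclude couples from the final analysis with no safety exception, and F4 offers no safety population or table to override them. At the planned 5% exclusion and an assumed 10% risk, the loss is about one event in the azithromycin arm with no shift in the rate. A shift to 9.5% or 8.1% needs 10% or 25% of affected couples to leave, and both shares are assumptions.

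Three further inferences are not supported:
- That E5 expressly covers all enrolled couples. It sets no limit to completers, but it does not say this, and it does not say whether collection continues after withdrawal. The point needs only events recorded before exclusion.
- That laboratory contamination events would be lost through 2.f. E5 5.c describes a laboratory rate, not events per couple.
- That this bears on the pregnancy comparison. What 2.f does to the primary endpoint is a separate matter.

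**What to change.** - **D2 2.f and 2.h:** add that adverse events recorded up to withdrawal or cycle cancellation stay in the safety analysis.
- **F4:** add a table of adverse events by randomised arm covering all randomised couples, with counts, percentages and the risk difference with a 95% confidence interval. Use person-level denominators where they fit: women for yeast vaginitis, both partners for gastrointestinal effects. Show pelvic infection after transfer per couple with a transfer as well.

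The cost is a few sentences and one extra table, built from data that E5 5.e already places in REDCap. No new follow-up after withdrawal is needed, and the sample size stays at 356.

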Given the conflicting evidence toward benefit of routine antibiotic prophylaxis and IVF outcomes, a non-inferiority approach was selected to test our hypothesis that no prophylaxis is not inferior to routine antibiotic administration. A total sample size of 356 patients (178 per arm) was determined based on an average baseline clinical pregnancy rate of 41% within our practice in this population with a non-inferiority margin of 15%, 80% power, and using a one sided $\alpha=0.025$ while estimating a 5% drop out rate. Our practice completed approximately 500 fresh IVF cycles in 2016. Our exclusion criteria are broad and we do not anticipate patient recruitment to be difficult. We believe 356 patients is feasible and estimate a 14 month timeline to complete recruitment if we enroll 7 patients at minimum per week.

F2 Interim Monitoring and Early Stopping

Interim analysis will be performed according to the Haybittle-Peto approach at 50% enrollment and 75% enrollment. This study will be considered safe to continue if there is an absence in trend toward severe adverse maternal, pregnancy or laboratory outcomes in either group. The DSMB will also assess recruitment progress and will review for futility of the trial in the context of lack of adequate recruitment. Data will be formally analyzed at 50% enrollment and then every 6 months thereafter to assess for early termination of the study.

F3 Analysis Plan

See Table 1 for timetable of patient enrollment and analysis. Our practice is required to track patient demographic data and cycle outcome measures to report to the Society for Assisted Reproductive Technology. Data are recorded and tracked through Research Electronic Data Capture (REDCap). Data from enrolled patients will be exported and tracked in a separate secure REDCap dataset from our existing dataset. All of our outcome measures are routinely tracked, and no additional data query will be required to address potential confounders as listed in Table 2.

F4 Statistical Methods

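### Non-severe adverse events are worded as antibiotic reactions, with no common symptom question for both arms, so background symptoms are likely to be under-recorded in the no-antibiotic arm

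*Combined protocol and SAP*

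**What the plan says.** Four places describe non-severe events, and each ties them to the antibiotic.

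- **E5 5.c (definition):** "Non-severe adverse events include adverse effects of antibiotic administration including yeast vaginitis, abdominal pain, diarrhea, nausea and vomiting".
- **E5 5.d (reportable events):** "Reportable non-severe adverse events include yeast vaginitis, nausea and vomiting or other adverse reactions from antibiotic prophylaxis which the patients will report to their nurses". D2 2.e uses nearly the same formula.
- **E5 5.a (the only active question):** patients are asked about taking the medication and "if any adverse side effects were incurred including yeast vaginitis, nausea and vomiting or other adverse reactions from antibiotic prophylaxis".

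Two other places are broader.

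- **E5 5.f:** "Patients will be instructed to report any adverse symptoms to their respective nurse or doctor".
- **E5 5.e:** "Adverse events will be noted in the patients chart and in the redcap database for complete capture and tracking".

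The trial is open-label. D3 3.f rules out blinding of patients and a placebo, and D2 2.d leaves providers and nurses unblinded. Sections E2 to E5 describe no symptom checklist and no assessment time common to both arms.

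**The concern.** Nausea, abdominal pain and diarrhea are non-specific and can occur in an IVF cycle with or without azithromycin. A patient who took azithromycin and feels sick fits the wording of 5.c and 5.d directly. One with the same symptom in the no-antibiotic arm does not obviously fit, and the compliance part of the 5.a question has nothing to refer to for that couple. The nurse who receives the report knows the arm. Following the plan as written is therefore likely to give fuller records in the antibiotic arm.

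At stake is the comparability of the side-effect data. Avoiding side effects is part of the argument for withholding prophylaxis: D2 2.b says of participants, "They may be spared from experiencing potential adverse side effects of the oral antibiotic". The DSMB is to review adverse events at 50% enrollment and every 6 months afterwards (5.b, 5.e), and its review is not limited to severe ones. If background symptoms are captured unequally, a by-arm table cannot show how much of a difference is due to azithromycin.

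**Working it through.** **1. The plan's own figure.** The documents state no figure for side effects. The related design figure is the sample size in F1: 41% in both arms, margin 15 points, one-sided alpha 0.025, power 80%, dropout 5%.

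n per arm = (1.960 + 0.842)² × 2 × 0.41 × 0.59 / 0.15² = 168.8, rounded up to 169. Then 169 / 0.95 = 177.9, rounded up to 178 per arm and 356 in total. This reproduces F1, and nothing below changes it.

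**2. The passages side by side.**

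| Section | Whose symptoms | Tied to the antibiotic? | How obtained |
|---|---|---|---|
| 2.e, 5.d | Not limited by arm | Yes | Patient reports to nurse (5.d) |
| 5.a | Patients generally | Yes, and joined to compliance | Asked, time not stated |
| 5.c | Not limited by arm | Yes | Definition only |
| 5.f | Patients generally | No | Spontaneous report |
| 5.e | Not limited by arm | No | Entered in chart and REDCap |

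Section 5.f is broader than the others, and the plan does not say which wording governs what is entered in REDCap. The symptom lists also differ: 5.c names abdominal pain and diarrhea, while 2.e, 5.a and 5.d do not.

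**3. Size of the possible bias.** Let b be the background rate in both arms, d the true added rate from azithromycin, and s the share of background symptoms recorded in the no-antibiotic arm. Assume full recording in the antibiotic arm.

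Recorded excess = (b + d) − s × b = d + b × (1 − s)

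The bias is b × (1 − s). It is 0 when s = 1 and reaches b only when s = 0.

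The documents give none of b, d or s. The table assumes d = 0, 178 per arm and one record per couple. Each cell shows the spurious excess in points, then the chance of two-sided P<0.05. That chance is Φ[(excess − 1.96 × SE₀) / SE₁], with SE₀ pooled and SE₁ unpooled.

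| Assumed b | s = 75% | s = 50% | s = 25% | s = 0 (bound) |
|---|---|---|---|---|
| 5% | 1.25; 8% | 2.5; 24% | 3.75; 53% | 5; 86% |
| 10% | 2.5; 13% | 5; 43% | 7.5; 84% | 10; 99% |
| 20% | 5; 24% | 10; 76% | 15; 99% | 20; over 99% |
| 30% | 7.5; 36% | 15; 93% | 22.5; over 99% | 30; over 99% |

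Worked cell, b = 10% and s = 50%: the recorded rates are 10% and 5%. SE₀ = √(2 × 0.075 × 0.925 / 178) = 0.0279, and SE₁ = √((0.10 × 0.90 + 0.05 × 0.95) / 178) = 0.0278. Then (0.05 − 1.96 × 0.0279) / 0.0278 = −0.17, which gives 43%.

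**The case against.** A reader might infer that a couple in the no-antibiotic arm cannot have a non-severe event, so that this arm has no background rate and every side-effect comparison is biased by the full background rate. The documents do not support that.

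- Sections 5.c and 5.d say what the events include, which is not an exclusive definition.
- Section 5.f covers any adverse symptom in all patients, and 5.e records events without limit by arm. Capture in the no-antibiotic arm may be lower, but it need not be zero.
- A strictly causal definition, applied equally, would exclude background symptoms from both arms and leave the true excess. Bias needs unequal capture, or background symptoms credited to the drug in the antibiotic arm. The documents quantify neither.

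The comparison is also not a planned analysis. The aims, the outcomes in D1 and the analyses named in F4 include no comparison of side effects. The continuation criterion in F2 is an "absence in trend toward severe adverse maternal, pregnancy or laboratory outcomes in either group", so non-severe symptoms do not enter it. The remark in 2.b on sparing patients side effects belongs to ethical considerations and is not a hypothesis.

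All of this stands, and it limits the point to likely under-recording of unknown size. It does not remove the point. Section 5.f relies on unprompted reports to unblinded nurses, offers no common question or timing, and conflicts in scope with the four places that describe the events.

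**Conclusion.** The point holds as a weakness of ascertainment. Attribution to the antibiotic is built into 2.e, 5.a, 5.c and 5.d, the one active question is joined to compliance, and nobody who reports or receives symptoms is blinded. Background symptoms are therefore likely to be under-recorded in the no-antibiotic arm, and a by-arm summary would tend to overstate the side effects of prophylaxis.

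The bias lies between 0 and the full background rate, and the documents do not allow it to be placed within that range. The tabulated figures rest on assumed background rates of 5% to 30%, assumed capture rates, and full recording in the antibiotic arm. The sample size, the primary analysis and the named secondary analyses are unaffected. The change is worth making because it is cheap and because symptoms not asked about at the time cannot be reliably recovered later.

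**What to change.** 1. In 2.e, 5.a, 5.c and 5.d, use one symptom list (nausea, vomiting, diarrhea, abdominal pain, yeast vaginitis, other). Define a non-severe event as any of these in either arm, whatever the presumed cause. This brings the four places into line with 5.f.
2. In 5.a, separate the symptom question from the compliance question. Ask both arms the same short checklist, covering the same period, at the same existing visit, for example egg retrieval. State how couples who do not reach that visit will be asked.
3. In 5.e, enter the checklist in REDCap and record presumed attribution in a separate field.
4. In 5.e or F4, state that these events will be summarised by randomised arm, including for the DSMB.

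The cost is one short form and a few minutes per couple, with no added visit. Reporting bias from the open-label design would be reduced but not removed, and any by-arm summary should say so.
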